2.2 Randomization Methodology

A total of 80 subjects are to be randomly assigned in a 1:1 ratio to one of two arms using permuted block randomization: (1) placebo or (2) famotidine. Subject randomization will be stratified by NYHA/WHO Functional Class (NYHA/WHO Functional Class II versus Class III/IV) to ensure balanced representation of this important marker of severity. A randomization code will be computer-generated by contract research organization (CRO) Axio Research, LLC. Subjects meeting study entry criteria will be randomized via an interactive web response system (IWRS). The randomization schedule will be generated by the randomization statistician at Axio Research (who is not on the project team) or designee and maintained in a secure and limited-access location separate from the study investigator and members of the project team. The study subject, investigative staff, the Sponsor, the Sponsor study team (includes contractors and vendors), excluding the unblinded study site pharmacist will be blinded to treatment assignments during the study.

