6 STATISTICAL METHODS

6.1 Sample Size Justification

The primary endpoint is the change in six-minute walk distance (6MWD). The study was powered to detect a difference of 31.9 meters. A 31.9 meter improvement in 6MWD is well aligned with established thresholds for a minimally important difference in patient reported outcomes (Mathai SC, et al. Am J Respir Crit Care Med, 2012; 186(5):428-433). The 6MWD was chosen because it is a surrogate for patient-centered outcomes and was the primary endpoint in labeling trials for most of the medications used to treat pulmonary arterial hypertension (PAH).

Standard deviation in 6MWD among PAH participants with NYHA functional class II, III, or IV symptoms is 37.6 meters (national Pulmonary Hypertension Association Registry; unpublished data). As shown, the proposed sample size has adequate power (0.96) to detect a minimally important difference in 6MWD even with 10% attrition in the study sample (power, 0.94).

Table 6-1: Power to detect a minimally important difference in 6MWD (31.9 meters)

Alpha	Sample size per group	Power for the total sample size	Sample size per group with ~10% attrition	Power with attrition
0.05	20	0.74	18	0.69
0.05	40	0.96	36	0.94
0.05	60	0.99	54	0.99

The field is appropriately shifting toward larger event driven trials; however, we did not feel a larger event driven trial of famotidine was warranted at this juncture. The current proposal is the first randomized evaluation of this drug and this pathway in individuals with right heart failure and/or PAH and a smaller Phase II trial was felt to be a more appropriate next step.

For the RHC sub-study, the initial sample size was set at 10 participants based on the following power to detect large differences.

Size of difference	SV index (mL/m2)	Total sample size	n per group	power
Large	20	10	5	0.87
Medium-high	15	10	5	0.67
Medium-low	10	10	5	0.36
Small	5	10	5	0.13

For the exercise sub-study, the initial sample size was set at 10 participants based on the following power to detect large differences.

Size of difference	VO2 (mL/min/kg)	Total sample size	n per group	power
Large	8	10	5	0.96
Medium	4	10	5	0.46
Low	2	10	5	0.15

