6.2 General Statistical Methods

6.2.1 General Methods

All outputs will be incorporated into Microsoft Excel or Word files, sorted and labeled according to the International Conference on Harmonization (ICH) recommendations, and formatted to the appropriate page size(s).

Tabulations will be produced for appropriate demographic, baseline, efficacy and safety parameters. For categorical variables, summary tabulations of the number and percentage within each category (with a category for missing data) of the parameter will be presented. For continuous variables, the mean, median, standard deviation, minimum and maximum values will be presented.

Formal statistical hypothesis testing will be performed with all tests conducted at the 2-sided, 0.05 level of significance. Summary statistics will be presented, as well as 95% confidence intervals on selected parameters, as described in the sections below.

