6.4.1.1 Sensitivity analysis

Sensitivity analyses will be performed using the PPS1 and PPS2 analysis sets instead of FAS.

Although every effort will be made to avoid missing data, a range of approaches to missing 6MWD will be considered as sensitivity analyses representing a range of conservative and anti-conservative biases to describe the range of possible differences.

Sensitivity analyses of the primary endpoint will include:

- 1) • a linear regression model using a worst case scenario (WCS) method of imputation
- 2) • a linear regression model of the 24 week 6MWD without imputation (complete case analysis)

(1) The worst case scenario method of imputation will impute zero for all missing 6MWD at week 24.

(2) The linear regression method will model the 24 week 6MWD on treatment assignment, adjusting for baseline 6MWD and baseline NYHA functional class using least squares and robust standard error estimates.

For all methods, treatment effect estimates and 95% CIs will be presented.

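### The worst-case sensitivity analysis sets missing walks to 0 m in both arms, so it does not bound the treatment effect

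*SAP*

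**What the plan says.** SAP 6.4.1 makes multiple imputation the primary handling of a missing week-24 6-minute walk distance (6MWD) in participants who are alive, and gives zero to those known to have died. SAP 6.4.1.1 then lists sensitivity analyses, described as "representing a range of conservative and anti-conservative biases to describe the range of possible differences". Two of them address missing walks:

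- The worst case scenario: "The worst case scenario method of imputation will impute zero for all missing 6MWD at week 24". Protocol 9.4.2 has the same rule.
- A complete case regression.

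The other two repeat the analysis in the per-protocol sets PPS1 and PPS2, which changes who is analysed, not how missing walks are handled. An estimate and 95% confidence interval are to be given for every method. No arm-specific, delta-adjusted or tipping-point analysis is planned.

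**The concern.** Deaths already count as zero in the primary analysis. What the worst-case rule adds is a zero for every living participant without a week-24 walk, whichever arm they are in. A bound on a treatment difference needs the arms treated differently: missing values bad in one arm and not in the other. Penalising both alike leaves the difference nearly unchanged when losses are equal. When they are not, the difference moves in whichever direction the loss counts happen to point.

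At stake is how a positive primary result would be read. The zero rule is the only planned analysis that makes missing walks in living participants worse than the imputation model predicts. If it is taken as the adverse limit, a reader may think robustness has been shown when no assumption unfavourable to famotidine was ever tried.

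**Working it through.** **Inputs from the documents.**
- Test level: "Formal statistical hypothesis testing will be performed with all tests conducted at the 2-sided, 0.05 level of significance" (SAP 6.2.1).
- Effect: "The study was powered to detect a difference of 31.9 meters" (SAP 6.1).
- SD: "Standard deviation in 6MWD among PAH participants with NYHA functional class II, III, or IV symptoms is 37.6 meters" (SAP 6.1), used here as the SD behind SAP Table 6-1.
- Size: "A total of 80 subjects are to be randomly assigned in a 1:1 ratio to one of two arms" (SAP 2.2), so 40 per arm.
- Attrition: about 10%, leaving 36 per arm (SAP Table 6-1).

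**Assumption.** The documents give no mean 6MWD. I take a placebo mean M of 250 to 450 m, with 400 m for illustration and a famotidine mean of M + 31.9. The only related figure is the 50 m entry minimum (protocol 5.1).

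**Step 1: the plan's own power.** Two-sample t-test, noncentrality 31.9 / (37.6 × √(2/n)).
- n = 40: 31.9 / 8.41 = 3.79, power 0.963 (SAP: 0.96).
- n = 36: 31.9 / 8.86 = 3.60, power 0.944 (SAP: 0.94).

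Table 6-1 reproduces.

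**Step 2: equal losses, zeros in both arms.** With 4 of 40 missing per arm, the difference is 0.9 × (M + 31.9) − 0.9 × M = 0.9 × 31.9 = 28.7 m, whatever M is.

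**Step 3: arm-specific extremes, same losses.**
- Famotidine missing at 0 m, placebo missing at the placebo mean: 0.9 × (M + 31.9) − M = 28.7 − 0.1M.
- Placebo missing at 0 m, famotidine missing at the famotidine mean: (M + 31.9) − 0.9M = 31.9 + 0.1M.

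| Assumed M (m) | Zeros in both arms | Against famotidine | For famotidine |
|---|---|---|---|
| 250 | +28.7 | +3.7 | +56.9 |
| 300 | +28.7 | −1.3 | +61.9 |
| 400 | +28.7 | −11.3 | +71.9 |
| 450 | +28.7 | −16.3 | +76.9 |

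The planned rule sits inside this range and reaches neither end.

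**Step 4: unequal losses.** With mF famotidine and mP placebo walks missing, the estimate is (1 − mF/40) × 31.9 + ((mP − mF)/40) × M. At M = 400:
- mF = 2, mP = 4: 30.3 + 20 = 50.3 m.
- mF = 4, mP = 2: 28.7 − 20 = 8.7 m.

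The imbalance term is M/40 per extra placebo loss: 7.5 m at 300 m, 10 m at 400 m, 11.3 m at 450 m. Imbalance is ordinary. If 8 of 80 are missing regardless of arm, the chance of an exact 4/4 split is C(40,4)² / C(80,8) = 0.29, and the chance that placebo loses more is (1 − 0.29)/2 = 0.36.

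**Step 5: precision.** With a fraction f missing at random in each arm, the effect is (1 − f) × 31.9 and the SD is √((1 − f) × 37.6² + f(1 − f) × M²). At f = 0.10 and M = 400, the SD is √(1272 + 14400) = 125 m against 37.6 m, and the SE is 125 × √(2/40) = 28 m for an effect of 28.7 m. By normal approximation at 40 per arm:

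| Missing per arm | M = 250 | M = 300 | M = 350 | M = 400 | M = 450 |
|---|---|---|---|---|---|
| 10% | 0.34 | 0.26 | 0.21 | 0.18 | 0.15 |
| 2.5% (one per arm on average) | 0.73 | 0.64 | 0.56 | 0.48 | 0.42 |

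Simulation of the planned regression at 10% random missingness (baseline SD of 100 m assumed) agrees: 0.26 at 300 m and 0.18 at 400 m. Power also depends on the realised split. At 400 m it is about 0.01 when losses are exactly 4/4, and roughly 0.35 to 0.4 when they are exactly 1/1.

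**The case against.** The strongest defence is that the label has a consistent meaning in this plan: worst for the participant. The secondary endpoints follow the same pattern (TAPSE zero, emPHasis-10 score 50, functional class IV, care escalated), and zero matches the primary rule for deaths. Read that way, it is a recognisable composite-type strategy. This stands as a reason to keep the analysis. It does not make it a bound on the treatment difference, which is the aim stated in SAP 6.4.1.1.

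The plan also has multiple imputation, complete case, two per-protocol sets and a responder analysis that counts missing as failure. Follow-up continues after study drug is stopped, which should limit missing data. All true, but none of these treats missing famotidine walks worse than missing placebo walks.

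A reader might infer two stronger points that the documents do not support:

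- **That the analysis has almost no power.** This depends on a mean walk the documents do not give, on the number missing and on the split. The analysis is also reported as an estimate with an interval, with no pass/fail rule, so the planned 0.94 is not its benchmark.
- **That the rule is biased toward famotidine.** The shift is conditional and symmetric. With arm-independent 10% missingness and no true effect, simulated type I error was 0.05. The 50 m estimate for the 2/4 split has an SE of about 26 m, so its interval runs from about 0 to 100 m. A false significant result becomes likely only with extreme splits: at 400 m about 62% of simulations for 1/7, against about 5% for 2/6.

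**Conclusion.** The point holds as a mismatch between the stated aim and the method. Zero in both arms does not bound the treatment effect: at 4 missing per arm and an assumed 400 m mean it gives about +29 m, inside arm-specific extremes of about −11 to +72 m. The width of that range scales with the assumed mean. At 250 m the lower end stays just above zero, so whether the adverse extreme reverses the sign depends on data not yet seen.

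The loss of precision is real at the planned 10% attrition (power roughly 0.15 to 0.34 for means of 450 to 250 m) but secondary. The primary estimate is not affected. This is a cheap improvement that should be made, not a flaw that invalidates the plan.

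**What to change.** Keep multiple imputation as the primary analysis, with deaths at zero as in SAP 6.4.1. Add one of the following to SAP 6.4.1.1:

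- **Delta-adjusted tipping point (preferred).** Lower the imputed week-24 values of living famotidine participants by 0, 25, 50, … m, leave placebo as imputed under the primary model, and report the delta at which the 95% confidence interval includes zero. With 4 of 40 missing, each 25 m step moves the estimate by only (4/40) × 25 = 2.5 m, so run the grid until the interval includes zero or imputed walks reach 0 m. The subtraction can be done on the imputed data sets before the regression, so the imputation step itself need not change. The listed imputation predictors do not include treatment arm, so state that delta is measured from the primary model's imputations.
- **Arm-specific extremes.** Missing living famotidine participants at 0 m with missing living placebo participants at the observed placebo mean. Then the reverse: placebo at 0 m and famotidine at the observed famotidine mean.

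The both-arms-zero analysis may stay, but should not be described as the worst case for the treatment effect. The secondary endpoints' worst-case rules (SAP 6.4.2.1 to 6.4.2.6) have the same symmetric form and should be checked at the same time. The cost is a few lines of code and one more sensitivity table to report.

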6.4.1.2 Additional analyses

Additional analyses of the relative change in 6MWD will include the proportion of participants who achieve a minimally important change in 6MWD of 31.9 meters or greater. To test the null hypothesis that there is no difference between the treatment groups, logistic regression adjusted for the NYHA functional class (stratification variable) will be used. The odds ratio between treatment groups will be provided with associated 95% CI. Subjects missing the 24 week 6MWD will not be counted as having achieved a minimally important change.

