6.4.1 Primary efficacy analysis

The primary endpoint is the difference between treatment groups in the change of 6-minute walk distance (6MWD) between baseline and 24 weeks. Linear regression will be performed for the FAS with the change in 6MWD between baseline and 24 weeks as outcome and treatment group as the primary predictor of interest, adjusted for baseline 6MWD and baseline NYHA functional class as the stratification variable. The estimate of the treatment effect will be provided with associated 95% confidence interval (CI).

Missing 6MWD at 24 weeks will be imputed as follows. Subjects known to be dead before the 24 week assessment will have zero imputed for their 24 week 6MWD. Missing 24 week 6MWD for subjects who are alive will be imputed using multiple imputation. The imputation model will have prognostic variables as the predictor variables. Prognostic variables will include age, gender, and etiology of pulmonary hypertension, baseline six minute walk test distance, baseline right ventricular diameter, and baseline BNP. The multiple imputation will use Markov Chain Monte Carlo (MCMC), which assumes that the variables in the imputation model have a joint multivariate normal distribution (MVN). The number of imputations to be performed will be 100. One hundred is selected because it is not too large that it requires heavy computations

and is not too small (such that the Monte Carlo error is still small enough at around 0.1 times the standard deviation). The “proc mi” procedure in SAS will be used to impute the missing observations.

PAH etiology in the analysis will be as follows:

- Idiopathic
- Familial
- Congenital Heart Disease
- Collagen Vascular Disease
- Toxin
- Portopulmonary Hypertension

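### The supportive 31.9 m responder model leaves out baseline 6MWD, which the primary model of the same change includes; adding it costs almost nothing and would recover a little power if baseline predicts change

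*SAP*

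**What the plan says.** SAP 6.4.1.2 (Additional analyses) splits the week-24 change in 6MWD at 31.9 m and compares the proportions reaching that gain. The model is specified as "logistic regression adjusted for the NYHA functional class (stratification variable) will be used", and the result is an odds ratio with 95% CI. A participant without a week-24 walk counts as not having reached the gain. Protocol 9.4.2 (Additional Analyses of the Primary Endpoint) names the same single covariate.

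The primary linear model of the same change, in SAP 6.4.1, is "adjusted for baseline 6MWD and baseline NYHA functional class as the stratification variable". The complete-case sensitivity model in SAP 6.4.1.1 uses the same two covariates. SAP 6.4.1 also lists baseline walk distance among the prognostic variables for the imputation model.

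SAP 6.2.3 requires the baseline value of the outcome in models for continuous outcomes. It states no such rule for binary outcomes.

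**The concern.** Whether someone gains 31.9 m may depend on where they start, for example through regression to the mean. The plan allows for this when change is analysed as a continuous variable but not when the same change is cut at a threshold.

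Two things are at stake, both modest. If baseline predicts change, the responder test has less power than the same data allow. And if the arms happen to differ in baseline 6MWD within NYHA strata, the primary estimate is adjusted for that and the responder estimate is not, so the two may drift apart for a reason unrelated to treatment.

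**Working it through.** **Inputs from the documents.** SAP 6.2.1 has "all tests conducted at the 2-sided, 0.05 level of significance". SAP 2.2 has "A total of 80 subjects are to be randomly assigned in a 1:1 ratio to one of two arms", so 40 per arm. SAP 6.1 has "The study was powered to detect a difference of 31.9 meters" and "Standard deviation in 6MWD among PAH participants with NYHA functional class II, III, or IV symptoms is 37.6 meters".

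**Reproducing the plan's power.** Treat 37.6 m as the SD of the analysed change.
- 40 per arm: SE = 37.6 × √(2/40) = 8.41 m; 31.9/8.41 = 3.79; normal approximation Φ(3.79 − 1.96) = 0.967; two-sample t-test 0.963. SAP Table 6-1 states 0.96.
- 36 per arm: normal approximation 0.949, t-test 0.944. The table states 0.94.

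The t-test reproduces the other rows of the table as well. The table therefore uses 37.6 m as the SD of the compared quantity, although the text calls it the SD of 6MWD.

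**Responder rates these inputs imply.** Assume normally distributed change and a placebo mean change of 0.
- Placebo: 1 − Φ(31.9/37.6) = 0.198. Famotidine: 1 − Φ(0) = 0.500.
- Pooled proportion 0.349; null SE = √(0.349 × 0.651 × 2/40) = 0.107; alternative SE = √((0.198 × 0.802 + 0.500 × 0.500)/40) = 0.101.
- Unadjusted power = Φ((0.302 − 1.96 × 0.107)/0.101) = 0.82.

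The documents give no power figure for this analysis.

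**Adding baseline 6MWD.** This was simulated with 80 subjects, 6,000 trials per scenario and a Wald test. Assumptions not in the documents: half of subjects in Class III/IV, a latent baseline-NYHA correlation of -0.4, no missing data, and the baseline-change correlation in the first column. The true effect is 31.9 m. The Monte Carlo SE of each power is about √(0.82 × 0.18/6000) = 0.005. Arrows run from NYHA only to NYHA plus baseline 6MWD.

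| Correlation | Power | Median log OR | Median SE |
|---|---|---|---|
| 0 | 0.824 → 0.821 | 1.447 → 1.475 | 0.520 → 0.529 |
| -0.2 | 0.820 → 0.823 | 1.449 → 1.508 | 0.521 → 0.537 |
| -0.3 | 0.821 → 0.838 | 1.455 → 1.554 | 0.523 → 0.550 |
| -0.5 | 0.829 → 0.872 | 1.470 → 1.760 | 0.525 → 0.597 |
| -0.6 | 0.822 → 0.899 | 1.469 → 1.911 | 0.528 → 0.638 |

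A repeat simulation gave 0.81 → 0.87 at -0.5, hence a gain of 4 to 6 points there. With no true effect, both models reject in about 4 to 5% of trials.

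**Where the gain comes from.** The SE rises in every row. Power increases because the conditional odds ratio moves further from 1 than the SE grows. At -0.5 the ratio of estimate to SE goes from 1.470/0.525 = 2.80 to 1.760/0.597 = 2.95. For the model-standardised risk difference the spread does shrink: its SD is about 3% lower at -0.3 and about 6% lower at -0.5.

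**Chance imbalance.** One SE of the baseline difference between arms is √(2/40) = 0.224 SD. It shifts the difference in mean change by |correlation| × 37.6 × 0.224:
- at -0.3: 2.5 m
- at -0.5: 4.2 m

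In about 14 to 15% of simulated trials famotidine started more than one SE higher, despite NYHA stratification. In those trials the mean risk difference with NYHA alone was about 0.26 (correlation -0.3) or 0.25 (-0.5). With baseline added it was 0.30, the true value. The opposite imbalance, about equally frequent, inflated it to 0.33 or 0.36 with NYHA alone.

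**The case against.** The case for leaving the plan as it is has several parts.

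- **No inconsistency.** A reader might infer that the SAP breaks its own covariate rule. It does not: SAP 6.2.3 states the rule for continuous outcomes, and this outcome is binary. The binary escalation endpoint (SAP 6.4.2.6) is also adjusted for NYHA class only, and protocol and SAP agree on the covariate. This stands in full.
- **No loss of precision in the reported odds ratio.** A reader might infer that adjustment would narrow its interval. On the log scale it would widen it. This stands; precision improves only for a standardised risk difference.
- **Imbalance is partly handled already.** The outcome is a change, so baseline has been subtracted, and NYHA class is used in both the randomisation and the model. This stands in part: subtraction does not remove an association between baseline and change, and NYHA is an imperfect proxy for walk distance.
- **The analysis is supportive.** A reader might infer that it carries the judgement on the minimally important difference. The primary comparison is the one powered at 31.9 m, and its adjusted estimate and CI can be read against that value directly.
- **Other causes of disagreement remain.** Dichotomising, and counting missing walks as non-response where the primary analysis uses multiple imputation for survivors, can separate the two results too. The extra covariate changes neither.
- **The size rests on an unknown correlation.** At 0.2 or below in absolute value the power gain is negligible, and the documents contain no data showing a ceiling effect.

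**Conclusion.** The omission is real and appears in both documents, but it is a missed efficiency and not an error. The NYHA-only test holds its level. If baseline 6MWD predicts change, that model gives up some power and leaves the residual baseline-change association unadjusted. The gain from adding baseline is about 0 points of power at a correlation of 0, about 2 at -0.3 and 4 to 6 at -0.5.

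These figures assume 40 per arm, an SD of change of 37.6 m, a placebo mean change of 0, no missing data and a true effect of 31.9 m. The correlation is assumed throughout. The documents do not support saying that chance imbalance goes wholly uncorrected, or that the present test is invalid. Severity is low.

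**What to change.** Before unblinding, in SAP 6.4.1.2 and Protocol 9.4.2:

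1. Add baseline 6MWD as a continuous covariate beside NYHA stratum in the logistic model.
2. Report the model-standardised risk difference with 95% CI next to the odds ratio, and name the variance method (delta method or bootstrap, for example).
3. State that the odds ratio is now conditional on baseline 6MWD and NYHA class, so it is not the same quantity as one adjusted for NYHA class alone.
4. Record the change in SAP Section 7 if the protocol text is not amended.

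The cost is small. Baseline 6MWD is already collected for every participant and already in the primary model. The additions are an assumption of linearity on the logit scale and one extra summary measure with its own variance calculation. If baseline turns out not to predict change, power is essentially unchanged (0.824 against 0.821 at a correlation of 0, within simulation error). Timing matters, because adding the covariate after unblinding would look data-driven.
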